5.0 Study Drug

5.1 Description

The study drug is the commercial product, Neurontin® (gabapentin) 250 mg/5 ml by Pfizer/Parke Davis. The active drug is in a flavored glycerin based solution.

The placebo will be also be a glycerin based clear solution that is flavored similar to the commercial product (see Section 5.4 below).

5.2 Treatment Regimen

Doses will be given in liquid form through gastrointestinal tubes (if the child already has one) or orally. Children will be put on the following dosage regimen:

Day	Morning	Afternoon	Evening
1 - 3			5 mg/kg
4 - 6	2.5 mg/kg	2.5 mg/kg	5 mg/kg
7 - 9	2.5 mg/kg	2.5 mg/kg	10 mg/kg
10 - 12	5 mg/kg	5 mg/kg	10 mg/kg

13 - 15	5 mg/kg	5 mg/kg	15 mg/kg
16 - 18	7.5 mg/kg	7.5 mg/kg	15 mg/kg
19 - 21	7.5 mg/kg	7.5 mg/kg	20 mg/kg
22 - 28	10 mg/kg	10 mg/kg	20 mg/kg
29	7.5 mg/kg	7.5 mg/kg	20 mg/kg
30	7.5 mg/kg	7.5 mg/kg	15 mg/kg
31	5 mg/kg	5 mg/kg	15 mg/kg
32	5 mg/kg	5 mg/kg	10 mg/kg
33	2.5 mg/kg	2.5 mg/kg	10 ing/kg
34			5 ing/kg

35 - 37 off for 3 days then crossover

Weight			
Day	Morning	Afternoon	Evening
1 - 3			5 mg/kg
4 - 6	2.5 mg/kg	2.5 mg/kg	5 ing/kg
7 - 9	2.5 mg/kg	2.5 mg/kg	10
10 - 12	5 mg/kg	5 mg/kg	10 mg/kg
13 - 15	5 mg/kg	5 mg/kg	15 ing/kg
16 - 18	7.5 mg/kg	7.5 mg/kg	15 mg/kg
19 - 21	7.5 mg/kg	7.5 mg/kg	20 mg/kg
22 - 28	10 mg/kg	10 mg/kg	20 mg/kg
29	7.5 mg/kg	7.5 mg/kg	20 mg/lcg
30	7.5 mg/kg	7.5 mg/kg	15 mg/kg
31	5 mg/kg	5 mg/kg	15 mg/kg
32	5 mg/kg	5 mg/kg	10 mg/kg

5.3 Method for Assigning Subjects to Treatment Groups

A randomization table will be made before the study begins. Each patient added will be entered into their group as the randomization table dictates. This table will be kept in the pharmacy, and a copy will be maintained by the research coordinator to keep track of which group each subsequent subject will be assigned. Access to the table with patient names and doses of drug or placebo will be available in the pharmacy 24 hours x 7 days per week for safety precautions and unblinding.

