3.0 Study Design

3.1 General Study Design

The design of this study is a prospective, randomized, double blind, placebo-controlled, crossover clinical trial. The study will involve a 22-day medication/placebo titration period, 7-day stable dosing, 9-day taper and washout, followed by crossover. The length of the study is 12 months.

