4.4 Subject Recruitment and Screening

Gillette Children's Specialty Healthcare clinicians and nurses that treat children with neurological impairment will be informed of the study. Targeted clinics within Gillette include pediatric neurology, pediatric gastroenterology, and pediatric pain, along with other pediatric clinics that provide a model of chronic care for children with chronic complex medical conditions. If a patient is seen within a clinic that has been informed of the study, an introduction letter for the study will be handed out to potential candidate families. Database searches will also be conducted for potential

subjects. If a candidate is found in a database search, that family will be mailed the introduction letter, and receive a follow-up telephone call two weeks later to determine if the family is interested. The introduction letter will also contain contact information for the investigators and the clinical research coordinator.

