5.4 Preparation and Administration of Study Drug

The study drug and the placebo will be prepared in the Gillette Hospital Pharmacy. The study will also be registered with the Investigational Drug Service (IDS) pharmacy IDS #4109RO.

Neurontin (gabapentin) Oral Solution 250 mg/5 ml by Pfizer Labs

Appearance:	clear solution
Inactive ingredients:	glycerin, xylitol, purified water and artificial cool strawberry anise flavor.
Storage Requirements:	Must be refrigerated

Placebo formulation:

Appearance:	clear solution
Inactive ingredients:	see below
Storage Requirements:	Must be refrigerated

Placebo Ingredients

Ora Sweet Sugar Free (Paddock Labs)	0.5 ml
Strawberry Flavoring (Gallipot Labs)	0.2 ml
Licorice Flavoring (LorAnn Oils, Inc.)	0.05 ml
Raspberry Flavoring (Gallipot Labs)	2 ml
Sterile Water (Baxter)	15ml

Compound Instructions

1. Mix all flavoring ingredients and Ora Sweet Sugar Free in a prescription vial.
2. Add the sterile water and shake well.
3. Label and refrigerate with a 60 day expiration date

Stock Supply Label: Gabapentin Placebo Oral Solution

Refrigerate Control #
Exp: (60 days from compounding)

A sufficient amount would be dispensed for a 34 days' supply dependent on the weight of the patient.

The active or placebo drug will be dispensed on a randomized manner. A log of the patient name/weight/address/phone # 1 will be kept together with the control # of the active drug and placebo.

The blinded study code can only be broken upon a request of the Principal Investigator.

A dosing chart will be printed out for patient's family/caregiver for both the active drug and the placebo. Only a 34 days' supply will be dispensed at one

time: So if the placebo was dispensed for the first 34 days the next supply for 34 days (active drug) - the family would have to pick up the new supply.

The study treatment will be administered orally or via a gastrointestinal tube 3 times daily, with dose specified for the parent or guardian in a customized table for each study subject.

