5.8 Blinding of Study Drug

The Gillette Children's Specialty Healthcare pharmacy will assign subjects to either the study drug or placebo as per the randomization table as described in Section 5.3. The pharmacy will prepare and label the study drug or placebo with a coded control number indicating group assignment.

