6.0 Study Procedures

Outline of procedure plan

1. Recruitment from clinics including: chronic care, neurology, gastroenterology, and pain
2. History and physical examination completed as part of routine assessment and management for chronic irritability
3. Determine if evaluation for potentially treatable causes of chronic irritability has been completed.
4. Parental consent
5. Parental questionnaire #1 and NCCPC-R rating 3 typical irritable events
6. Randomization: gabapentin or placebo
7. Titration schedule
8. Day 6 — phone call by study staff (or closest week day)
9. Day 13 — NCCPC-R, questionnaire #2, and phone call follow-up (or closest week day)
10. Day 24 — NCCPC-R, questionnaire #2, and phone call follow-up (or closest week day)
If no improvement (dose 40 mg/kg/day) begin taper early(step #11) and set up visit with Research Coordinator (Step #12)
11. Day 29 — Begin medication taper
12. Day 34 to 38 — Family comes in to meet with the Research Coordinator. Subject is weighed. Perceived benefits and side effects of the drug are discussed. Report any concerns to the PI, if any. Subject is provided new drug at this visit. The old bottle will be taken back, along with the dosing chart. Remaining drug will be measured.
13. Day 38 — Crossover
14. Repeat steps 7 —11
15. At completion Research Coordinator contacts family by telephone to discuss perceived benefits/side effects of round 2 drug. Reports concerns to PI, if any

Parents complete one questionnaire #1, four questionnaires #2, and six NCCPC-R

Questionnaire # 1: includes 60 questions that require identifying the appropriate response from the items listed and 5 questions that require a written response.

Information obtained includes: frequency and duration of pain episodes along with associated gastrointestinal symptoms and sleep disturbance. The questionnaire takes approximately 15 minutes to complete.

Questionnaire #2: includes 24 questions that require identifying the appropriate response from the items listed and 2 questions that require a written response. Information obtained includes: frequency and duration of pain episodes along with associated gastrointestinal symptoms and sleep disturbance. The questionnaire takes approximately 5 minutes to complete.

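### The research coordinator, who discusses benefit and side effects with families, holds a copy of the randomization table, and the plan does not say the copy is masked

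*SAP*

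**What the plan says.** SAP Section 3.1 describes the trial as a "prospective, randomized, double blind, placebo-controlled, crossover clinical trial". Section 5.3 sets the allocation method: "A randomization table will be made before the study begins". The table is held in the pharmacy, and in addition "a copy will be maintained by the research coordinator to keep track of which group each subsequent subject will be assigned". The next sentence says: "Access to the table with patient names and doses of drug or placebo will be available in the pharmacy", at all hours, for safety and unblinding.

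The coordinator's other duties appear elsewhere. Section 4.4 says of recruitment: "The introduction letter will also contain contact information for the investigators and the clinical research coordinator". Section 6.0, step 12, has the family meet the coordinator at Day 34 to 38, where the child is weighed and the new bottle provided. Of that visit it says: "Perceived benefits and side effects of the drug are discussed. Report any concerns to the PI, if any". Step 15 has the coordinator telephone the family at completion on the same topics for the second-period drug.

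On masking, Section 5.8 has bottles labelled with a coded control number, and Section 5.9.3 has labels identical apart from a unique control number. Section 5.4 states: "The blinded study code can only be broken upon a request of the Principal Investigator". Section 8.4 limits access to the code to approved providers, a term the document does not define.

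**The concern.** The purpose given for the coordinator's copy looks forward: it is for following which group the next children will enter. Someone who speaks with families about how treatment is going should not hold the allocation list unless it is clearly masked. Someone who is a recruitment contact should not see the coming sequence at all.

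Two things are at stake. The first is blinding: in a two-period crossover, knowing a child's sequence gives away the treatment in both periods. The second is allocation concealment: the list shows upcoming assignments to a person whom families may contact about joining. The outcomes are caregiver reports and can respond to cues from staff. The side-effect information that the coordinator gathers and passes to the principal investigator could also be coloured by knowledge of the treatment.

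**Working it through.** No formula applies to who holds a list, and the plan gives no figure to reproduce. The check sets the sections side by side and then counts how far the exposure could reach.

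**1. Is the copy masked anywhere?**

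| SAP section | What it protects | Covers the coordinator's copy? |
|---|---|---|
| 5.3, sentence on access | Table with names and drug or placebo, available in the pharmacy | Not stated; may be a separate decoded list |
| 5.4 | Breaking of the code | No |
| 5.8 | Bottle label (coded control number) | No |
| 5.9.3 | Identical labels apart from the control number | No |
| 8.4 | Access to the code | Not stated |

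No section says what the copy shows.

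**2. What does each reading imply?**

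- *The copy shows treatment.* The coordinator knows both periods for every child. That contradicts Section 3.1 and bypasses the limit in Section 5.4. It also falls outside Section 8.4, but only if the coordinator is not an approved provider. Section 5.8 lends this reading some support, since the "pharmacy will assign subjects to either the study drug or placebo as per the randomization table as described in Section 5.3". This does not prove it, because the pharmacy could work from a coded table and a separate key.
- *The copy shows coded groups.* The coordinator is not unblinded by it, but the upcoming sequence is still disclosed in coded form. If the codes are stable group labels, a single unblinding would reveal every child with that label.

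**3. How many discussions are involved?** Section 6.0 names the coordinator in two discussions of benefit and side effects: step 12 (Day 34 to 38) and step 15 (completion). That is 2 per child, or 2 × 40 = 80 across the 40 planned evaluable subjects. Section 6.0 gives the Day 6 call to study staff and names no role for the Day 13 and Day 24 calls, so these are not counted.

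**4. Where do the ratings fall?** The Schedule of Events in Section 6.0 marks the NCCPC-R on Days 0, 13, 24, 34–37, 51 and 62. That makes 6, which agrees with the total in the procedure outline, and 6 − 1 = 5 are post-baseline.

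| Position relative to the coordinator visit | Rating days | Number |
|---|---|---|
| Before | 13, 24 | 2 |
| Within its window | 34–37 | 1 |
| After | 51, 62 | 2 |
| Total post-baseline | | 5 |

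An early taper brings the visit forward, but still after the Day 24 rating. Step 12 does not itself list a rating at the visit; the Day 34–37 entry comes from the Schedule of Events. The closing call follows Day 62, so no scheduled rating comes after it.

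Both treatment ratings of period 2 (Days 51 and 62) therefore follow a conversation with the coordinator. Each child's drug-versus-placebo contrast needs period 2.

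**The case against.** The best defence is that the copy is meant to be masked. Section 5.3 uses two descriptions: the coordinator follows the group, while the list with names and drug or placebo is the one available in the pharmacy for unblinding. Section 5.8 treats group as something coded. Sections 5.4 and 8.4 would have little purpose if the coordinator already held the answer. On this view there is an ambiguity and not a breach, and saying that the copy is coded would largely settle it. This stands to the extent that the document does not show the coordinator to be unblinded. It does not remove the point, because a coded copy still lays out the assignments to come.

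A second argument is that the harm is remote. Parents complete the NCCPC-R and the questionnaires, and nothing shows them to be unblinded. The Day 13 and Day 24 ratings precede any named coordinator discussion. No section gives the coordinator eligibility decisions, and every child is assigned both treatments, so foreknowledge could influence only treatment order or enrolment timing. A route to the Day 51 and Day 62 ratings needs an unmasked copy, some cue from the coordinator, and a lasting effect on the parent. All of this is fair and limits the severity. The 80 discussions measure reach, not bias.

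A third argument is that Section 5.8 describes the control number as indicating the group, so giving the coordinator a control number may seem to undo the remedy. Because that number is coded (Section 5.8) and unique (Section 5.9.3), it need not reveal the group to anyone without the key. The two sections do need consistent wording.

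**Conclusion.** The concern holds as a fault in a stated rule. Section 5.3 gives a family-facing role a copy of a pre-made allocation table in order to follow future assignments, and nothing masks that copy. Followed as written, it discloses the upcoming sequence even if coded, and it breaks the double blind if decoded. Which of the two applies cannot be settled from the document.

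The size of any bias cannot be derived. The reach is 2 named discussions per child, with 2 of the 5 post-baseline NCCPC-R ratings after the first discussion, 1 within its window, and none after the closing call. Any effect on the ratings would be indirect. The closing call could affect only reports of benefit and side effects. The case for change rests on a modest but avoidable risk that costs very little to remove; it should be fixed.

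**What to change.** Delete the clause in SAP Section 5.3 that gives the coordinator a copy, and replace it with:

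> The randomization table will be kept only in the pharmacy. The research coordinator will notify the pharmacy of each enrolment and will receive only a control number that does not reveal the group.

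Align Section 5.8 by stating that the link between control number and group is held by the pharmacy. The pharmacy's round-the-clock unblinding access stays as it is.

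If the coordinator must keep a list, a second-best option is to state that it carries no treatment or sequence identity and only assignments already made.

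The cost is almost nothing: one replaced clause in Section 5.3 and a small wording change in Section 5.8. The pharmacy already holds the table, assigns from it, prepares and labels the bottles, and provides unblinding (Sections 5.3, 5.8 and 8.4).

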5.4 Preparation and Administration of Study Drug

The study drug and the placebo will be prepared in the Gillette Hospital Pharmacy. The study will also be registered with the Investigational Drug Service (IDS) pharmacy IDS #4109RO.

Neurontin (gabapentin) Oral Solution 250 mg/5 ml by Pfizer Labs

Appearance:	clear solution
Inactive ingredients:	glycerin, xylitol, purified water and artificial cool strawberry anise flavor.
Storage Requirements:	Must be refrigerated

Placebo formulation:

Appearance:	clear solution
Inactive ingredients:	see below
Storage Requirements:	Must be refrigerated

Placebo Ingredients

Ora Sweet Sugar Free (Paddock Labs)	0.5 ml
Strawberry Flavoring (Gallipot Labs)	0.2 ml
Licorice Flavoring (LorAnn Oils, Inc.)	0.05 ml
Raspberry Flavoring (Gallipot Labs)	2 ml
Sterile Water (Baxter)	15ml

Compound Instructions

1. Mix all flavoring ingredients and Ora Sweet Sugar Free in a prescription vial.
2. Add the sterile water and shake well.
3. Label and refrigerate with a 60 day expiration date

Stock Supply Label: Gabapentin Placebo Oral Solution

Refrigerate Control #
Exp: (60 days from compounding)

A sufficient amount would be dispensed for a 34 days' supply dependent on the weight of the patient.

The active or placebo drug will be dispensed on a randomized manner. A log of the patient name/weight/address/phone # 1 will be kept together with the control # of the active drug and placebo.

The blinded study code can only be broken upon a request of the Principal Investigator.

A dosing chart will be printed out for patient's family/caregiver for both the active drug and the placebo. Only a 34 days' supply will be dispensed at one

time: So if the placebo was dispensed for the first 34 days the next supply for 34 days (active drug) - the family would have to pick up the new supply.

The study treatment will be administered orally or via a gastrointestinal tube 3 times daily, with dose specified for the parent or guardian in a customized table for each study subject.

5.5 Subject Compliance Monitoring

Compliance will be monitored by having the parents of the subject bring any unused drug back to Gillette Children's Specialty Healthcare each time they visit for the study. Amount of unused drug will be measured by the pharmacy before the subjects can get their next supply of study drug. Subjects will also be called every two weeks to assess any AEs and any positive effects subjects are experiencing. They will be asked how the customized drug plan for them is working. If a subject is found to be noncompliant with the study drug, the subject will be withdrawn from the study, with all withdrawal procedures followed. A subject will be defined as noncompliant if more than three days of doses of drug are missed.

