8.5 Stopping Rules.....	36
8.6 Medical Monitoring	36
9.0 Data Handling and Record Keeping	36
9.1 Confidentiality	36
9.2 Source Documents	37
9.3 Case Report Forms.....	37
9.4 Records Retention.....	37
10.0 Study Monitoring, Auditing, and Inspecting	37
10.1 Study Monitoring Plan.....	37
10.2 Auditing and Inspecting.....	38
11.0 Ethical Considerations	38
12 Study Finances	39
12.1 Funding Source	39
12.2 Conflict of Interest	39
12.3 Subject Stipends or Payments	39
13 Publication Plan	39
14 References.....	39
15 Attachments	40

List of Abbreviations

AE	Adverse Event
CFR	Code of Federal Regulations
CRF	Case Report Form
FDA	Food and Drug Administration
GCP	Good Clinical Practice
HIPAA	Health Insurance Portability and Accountability Act of 1996
ICH	International Conference on Harmonization
IDS	Investigational Drug Service
IRB	Institutional Review Board
ITT	Intent to Treat
NCCPC-R	Non-Communicating Children's Pain Checklist-Revised
PHI	Protected Health Information
REPA	Report of External Professional Activities
SAE	Serious Adverse Event
UPIRTSO	Unanticipated Problems Involving Risk to Subjects or Others

Study Summary

Title	A phase II, randomized, placebo-controlled, double blind, cross-over, study of the effects of Gabapentin on chronic irritability in neurologically impaired children
Short Title	Effects of Gabapentin on chronic irritability in neurologically impaired children.
Phase	Phase II
Methodology	The study is a randomized, placebo-controlled cross-over.
Study Duration	The estimated duration of the study is 12 months
Study Center(s)	This is a single center study to be conducted at Gillette Children's Specialty Hospital, [name].
Objectives	To determine if gabapentin provides symptom relief for chronic irritability in neurologically impaired children despite medical management for identified sources of symptoms or if no etiology is identified.
Number of Subjects	40 evaluable subjects
Diagnosis and Main Inclusion Criteria	Neurological impairment and chronic irritability suggesting pain.
Study Product, Dose, Route, Regimen	Gabapentin (Neurontin®), to be administered as an oral solution titrated over a 22 day period, followed by a 7 day stable dose period (40 mg/kg/day over 3 dosages), followed by a 9 day taper and washout period
Duration of administration	Subjects will receive drug for 34 days, and placebo for 34 days, with a 3 day washout period in between.

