4.5 Early Withdrawal of Subjects

4.5.1 When and How to Withdraw Subjects

Subjects may withdraw from the study at any time by withdrawing their consent. They must agree to be contacted (for safety reasons) for survival data. Subjects who do not adhere to the study drug dosing may also be withdrawn from the study to preserve the data collection.

If the subject withdraws from the study, it will be recommended to titrate off the medication per the chart depending on current dose.

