7.3 Subject Population(s) for Analysis

The subject population to be analyzed includes all protocol compliant subjects. Subjects who are not compliant with the protocol will be withdrawn as described in Section 5.5

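### The compliance rule ignores when doses are missed, so in period 2 a child can be dropped for doses missed after the last outcome form

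*SAP*

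**What the plan says.** - **Rule (SAP 5.5).** "A subject will be defined as noncompliant if more than three days of doses of drug are missed". The section does not say whether the count is per period or over both, whether the days must be consecutive, or which days matter.
- **Consequence.** Section 5.5: "If a subject is found to be noncompliant with the study drug, the subject will be withdrawn from the study". Section 4.5.1 is permissive: "Subjects who do not adhere to the study drug dosing may also be withdrawn from the study to preserve the data collection".
- **Analysis set (SAP 7.3).** "The subject population to be analyzed includes all protocol compliant subjects". No other analysis population is defined.
- **Measurement.** Section 5.5: "Amount of unused drug will be measured by the pharmacy before the subjects can get their next supply of study drug". Sections 5.9.3 and 6.0 add a dosing chart on which the caregiver marks each dose. Section 5.9.3 intends the chart to be reconciled with the volume.
- **Forms (SAP 6.0).** The numbered steps place NCCPC-R and Questionnaire #2 on Days 13 and 24 and repeat these after crossover. The Schedule of Events gives Days 51 and 62 for period 2 and adds a form at Days 34–37.
- **Dosing (SAP 5.2).** There are 34 dosing days per period. The target of 40 mg/kg/day runs over Days 22–28, and the taper over Days 29–34. Then: "35 - 37 off for 3 days then crossover".

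**The concern.** An adherence filter on an efficacy set should keep children whose outcome forms reflect the assigned treatment. A plain count of days cannot do this, because it treats a dose missed before a form and one missed after it alike.

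In a crossover, excluding a child loses the within-child comparison. Excluding a child for what happened after the last form discards valid, complete NCCPC-R and Questionnaire #2 data and gains nothing. It also makes membership of the analysed set depend on behaviour after the outcome is known to the family, such as easing off during the taper because the child did or did not improve.

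In the other direction, a gap that falls exactly on the first target-dose days passes the rule.

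**Working it through.** **1. Schedule totals (SAP 5.2).** Titration: three days each at 5, 10, 15, 20, 25, 30 and 35 mg/kg, 3 × 140 = 420. Target: 7 × 40 = 280. Taper: 35 + 30 + 25 + 20 + 15 + 5 = 130. Total 830 mg/kg over 34 days. The drug-free interval is 37 − 35 + 1 = 3 days, as the plan states.

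**2. Where the last period 2 form falls.** Crossover is on Day 38, so Day 62 is period day 62 − 37 = 25. That leaves 34 − 25 = 9 dosing days after the form (nominal, since calls may move to the closest weekday).

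**3. The rule applied to single gaps in one period.**

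| Days missed | Count | Rule | mg/kg missed | Relation to form |
|---|---|---|---|---|
| Period 2, days 31–34 | 4 | noncompliant | 25+20+15+5 = 65 (7.8%) | all after Day 62 |
| Period 1, days 22–24 | 3 | compliant | 120 (14.5%) | no target dose before or on Day 24 |

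Of the 31 possible four-day gaps in a period, 6 (starting on days 26 to 31) lie wholly after period day 25. Every one leads to exclusion.

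**4. Share of period 2 noncompliers who cross the limit only after the form.** Assume 34 scheduled days (no early taper), each missed independently with probability p, counted per period. Let A = P(Bin(34, p) > 3) and B = P(Bin(25, p) > 3). The share is (A − B)/A.

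| p | A | B | Share |
|---|---|---|---|
| 3% | 0.0183 | 0.0062 | 66% |
| 5% | 0.0881 | 0.0341 | 61% |
| 10% | 0.4462 | 0.2364 | 47% |

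**5. What this means for pairs at p = 5%.** Under the current rule counted per period, 1 − (1 − 0.0881)² = 16.8% of pairs are lost. If misses are counted only up to the Day 24 and Day 62 forms, P(Bin(24, 0.05) > 3) = 0.0298, and the loss is 1 − (1 − 0.0298)(1 − 0.0341) = 6.3%. Per 40 children, that is 6.7 against 2.5.

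**6. How often the Days 22–24 gap occurs among compliers.** Under the same model a complier who misses all three days has missed no other: 0.05³ × 0.95³¹ / (1 − 0.0881) = 0.00003. The case matters only if missed days cluster, and the plan gives nothing on clustering.

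**7. Does a Day 34–37 form exist?** The schedule table marks Questionnaire #2 on Days 13, 24, 34–37, 51 and 62, five in all; the text says four. The table marks NCCPC-R on Days 0, 13, 24, 34–37, 51 and 62, six in all; the text also says six. The numbered steps list no form at Days 34–37. The evidence conflicts, so the last form of period 1 is either Day 24 or Days 34–37.

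**The case against.** **The rule is an ordinary adherence threshold.** Counted per period it asks for 31 of 34 days (91%), and it also governs withdrawal. That is fair, but as the sole gate to the analysis it still discards forms that the missed doses could not have influenced.

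**Missed titration or taper days are not harmless.** This stands. Section 1.5 gives slow titration up and down a purpose, to limit side effects and withdrawal symptoms. The point concerns the efficacy forms only; such misses remain relevant to safety. A child who misses Days 1–4 departs from the titration before any form, and that exclusion is not challenged here.

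**The taper example is unsafe in period 1.** This also stands. If the Day 34–37 form exists, taper doses precede it. The example is therefore confined to period 2.

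**Readings that go too far.**
- A reader might infer that a three-day gap makes a child washed out by the plan's own standard, since the summary gives the same length: "with a 3 day washout period in between". But those three days follow a six-day taper, and the plan describes nine days of taper and washout together. It does not say that three days after an abrupt stop is a washout.
- A reader might infer a diluted treatment effect. Step 6 shows that independent misses produce almost none, and the documents support no figure for clustered gaps.
- A reader might say that compliance is judged by volume alone. Section 5.9.3 already reconciles the chart with the container; what is missing is its use in the 5.5 definition.

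**Conclusion.** The point holds in a limited form. Sections 5.5 and 7.3 together let doses missed after the last period 2 form remove a child with complete NCCPC-R and Questionnaire #2 data. That follows from the text and the schedule and needs no assumption about rates.

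The size does need one. With independent misses at 5% and a per-period count, about 61% of period 2 noncompliers are of this kind (66% to 47% at 3% to 10%). Real misses may cluster, and the forms may shift by a day or so.

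The converse case, no target dose before the Day 24 form yet compliant, is possible under the rule, but its frequency is unknown.

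The harm is avoidable loss and selection of pairs rather than a failure of power. With the plan's inputs (difference 15, SD 25, correlation 0.6) and an assumed two-sided 5% test, the SD of a difference is 25 × √(2 × 0.4) = 22.4, and power is about 99% with 40 pairs and 97% with 32.

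Whether to analyse compliant subjects only is a separate question, which this point leaves open.

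**What to change.** For the analysis set only:

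1. In 5.5 and 7.3, define compliance for each form: count missed days within the period, from the dosing chart, up to the form being analysed. Doses missed after the last form of a period then never exclude a child. Use returned volume as a cross-check through the 5.2 table.
2. Report exposure in the days just before each form descriptively or as a sensitivity analysis. Do not turn it into a strict cut. For example, requiring 80% of the scheduled dose over three days at 40 mg/kg fails anyone who misses one day (67%). At p = 5% it excludes 1 − 0.95³ = 14.3% of child-periods against 8.8% now, and 26% of pairs against 17%. At 3% it excludes 17% of pairs against 4%. It loses fewer only towards 10%.
3. Reconcile the Day 34–37 form between the schedule table, the numbered steps and the stated questionnaire counts, because it sets the last form of period 1.
4. Reconcile *may* (4.5.1) with *will* (5.5) on withdrawal. Whether a child stops treatment is for the clinical team.

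The cost is wording and entry of chart marks. Section 6.0 states that the chart is collected at the crossover visit; for period 2 it mentions only the bottle, so the return of the second chart should be written in. The small downside is reliance on caregiver-marked charts.
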